date (i.e., similar to the matched oxygen therapy patient in time from the fibrosing ILD diagnosis date to the index date, and during the same continuous enrollment period as the fibrosing ILD diagnosis date).

NOTE: Following review of results from Aim 1, the study team will determine whether continuous enrollment criteria for Aim 2 and Further Aim requires revision.

Variables:	
Aim 1
 
Outcomes: time to initiation of oxygen therapy; time to sustained oxygen therapy use; sustained oxygen therapy use within the first 12 months of follow-up
 
Baseline covariates: demographic characteristics (age, sex, race/ethnicity, geographic region, insurance type, index year), clinical characteristics (underlying ILD type; respiratory diseases; other clinical characteristics; Quan-Charlson comorbidity score; Agency for Health Research and Quality [AHRQ] comorbid conditions; smoking; pulmonary rehabilitation) healthcare utilization characteristics (provider specialty; medication use; all-cause HCRU; all-cause health care costs)
 
Stratification: IPF vs non-IPF ILD
 
Aim 2 [REDACTED]
 
Exposure: oxygen therapy vs no oxygen therapy
 
Primary Outcomes: Time to disease progression; time to all-cause mortality; time to hypoxemia, time to acute exacerbations, counts of acute exacerbations
 
[REDACTED]
 
Baseline covariates: demographic characteristics (index year, age, sex, race/ethnicity, geographic region, insurance type), clinical characteristics (underlying ILD type; respiratory diseases; other clinical characteristics; Quan-Charlson comorbidity score; AHRQ comorbid conditions; smoking; pulmonary rehabilitation) healthcare utilization characteristics (provider specialty; medication use; all-cause HCRU; all-cause health care costs)

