7.3 VARIABLES

Variables related to the study period will be defined as follows:

Aim 1

- **Fibrosing ILD diagnosis date**—The first ILD diagnosis date for patients with ≥ 2 fibrosing ILD diagnoses on different dates and within 365 days. The fibrosing ILD diagnosis date is the first day of follow-up observation time for Aim 1.
- **Pre-ILD baseline period**—The 12-month period prior to the fibrosing ILD diagnosis date.
- **Aim 1 follow-up period**—The variable period starting on the fibrosing ILD diagnosis date and continuing until the earliest of the following: disenrollment from the health plan, death, or end of the study period. The Aim 1 follow-up period will be used to assess Aim 1 outcomes.
 - **All-cause mortality**—Death will be used as a censoring event and is further defined in Section 7.3.3.1.

Aim 2

- **Index date**—For the oxygen therapy cohort, the first date following the fibrosing ILD diagnosis date with a claim with diagnosis for oxygen therapy; for the no oxygen therapy cohort, a date within the same continuous enrollment period as the fibrosing ILD diagnosis date that is similar to the matched oxygen therapy patient in time from fibrosing ILD to index date. The index date is the first day of follow-up observation time for Aim 2 and Further Aim.
- **Pre-index baseline period**—The 12-month period prior to the index date.
- **Aim 2 follow-up period**—The variable period starting on the index date until the earliest of the following: disenrollment from the health plan, death, or the end of the study period. Matched pairs will be given the same duration of follow-up. The Aim 2 follow-up period will be used to assess Aim 2 and Further Aim outcomes.
 - **All-cause mortality**—Death will be used as a censoring event and is further defined in Section 7.3.3.1.

An overview of the analytic study variables and the study periods for which each analytic variable will be reported is provided in Table 1. Additional variable information is provided in Sections 7.3.1 to 7.3.4.

Table 1. Analytic Variables by Data Source and Time Period

Characteristic	Data source		Aim 1 time period		Aim 2 time period	
	Claims*	EHR	Pre-ILD baseline	Follow-up	Pre-index baseline	Follow-up
Aim 1 outcomes						
Oxygen therapy (time to initiation, sustained oxygen therapy use)		X		X	X	
Aim 2 outcomes						
Disease progression	X	X				X
All-cause mortality	X					X
Hypoxemia	X	X	X		X	X
Acute exacerbations	X	X				X
Patient characteristics†						
Index year	X		X		X	

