7.3.3.2 Secondary Outcomes

- **Hypoxemia**—Sample size permitting, hypoxemia (i.e., oxygen saturation [SpO₂] <90%) will be captured as available in the database using specific ICD-10-CM codes or EHR data among the subset of patients with both claims and EHR in the Market Clarity database. Time to hypoxemia will be reported as time between index date and first evidence of hypoxemia.
- **Respiratory deterioration/Acute exacerbations**—An acute exacerbation of fibrosing ILD has been defined clinically as an unexplained worsening or development of dyspnea within 30 days in combination with a high-resolution CT indicating interstitial pneumonia, and excluding pulmonary infection, left heart failure, pulmonary embolism or other identifiable causes of acute lung injury.⁹ Based on these clinical criteria, acute exacerbations will be defined as follows:
 - ≥1 claim with procedure code for CT scan, and
 - Evidence of dyspnea, as defined by ICD-10-CM codes or EHR data in the integrated database, within 30 days prior to date of CT scan, and
 - No claims with diagnosis for pulmonary infection, left heart failure, pulmonary embolism, or other identifiable causes of acute lung injury within 30 days prior to date of CT scan.

The time to first exacerbation and population annualized counts of exacerbations (sum of all exacerbations for all individuals / sum of follow-up time [person years] for all individuals) will be described. Exacerbations occurring within 14 days of each other will be considered a single exacerbation episode. The start date of the exacerbation episode will be the service date of the first event (i.e., dyspnea or CT scan). The end date of the exacerbation episode will be defined as the last observed exacerbation event date (or discharge date if event occurs during an inpatient stay) + 14 days. Exacerbation episodes that include an inpatient stay will also be reported separately as exacerbations involving a hospitalization.

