7.3.5.2 Clinical Characteristics

- **Underlying ILD type**—Patients will be classified into the following underlying ILD types based on claims from the entire study period: autoimmune ILD, HP, sarcoidosis, unclassified ILD/IIP, and multiple. The underlying ILD type will be defined based on the presence of ≥ 1 specific ICD-10-CM diagnosis code for autoimmune ILD, HP, and sarcoidosis. Patients without any underlying ILD diagnosis will be classified into the unclassified ILD/IIP type. Patients with diagnoses for >1 underlying ILD types will be classified as multiple.
- **Respiratory diseases**—Separate indicator variables will be created for the presence of ≥ 1 diagnosis code in any position on a medical claim. The following conditions will be included: pulmonary hypertension, acute respiratory failure, asthma, COPD, pneumonia, lung transplantation, upper respiratory tract infection, lower respiratory tract infection, lung cancer, and cystic fibrosis.
- **Other clinical characteristics** – Similar to respiratory disease, a separate indicator variables will be created for the presence of ≥ 1 diagnosis code in any position on a medical claim. The following conditions will be included: gastroesophageal reflux disease (GERD), heart failure, and obstructive sleep apnea.
- **Quan-Charlson comorbidity score**—A comorbidity score will be calculated based on the presence of diagnosis codes on medical claims.^{10, 11} The Quan-Charlson comorbidity score will also be categorized into the following groups: zero, one to two, three to four, and five or more.
- **Comorbid conditions**—General comorbid conditions will be defined using the Clinical Classifications Software managed by the Agency for Healthcare Research and Quality (AHRQ).¹² This measure generates indicator variables for specific disease

conditions based on ICD-9-CM and ICD-10-CM diagnoses. The top 20 comorbid conditions will be presented.

[figure not shown]
- **Smoking**—An indicator variable will be created to identify patients with evidence of current or prior tobacco use based on diagnosis codes or pharmacy fills for smoking cessation treatments (bupropion, varenicline tartrate, or nicotine [inhalation, gum, lozenge, transdermal]).
- **Pulmonary rehabilitation**—Indicator and count variables will be created for the presence of procedure codes for pulmonary rehabilitation.

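### The visible plan defines no pre-index acute-exacerbation variable for Aim 2, so adjustment of the exacerbation comparison for exacerbation history cannot be confirmed and should be added unless Section 7.6.2 already provides it

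*Combined protocol and SAP*

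**What the plan says.** The abstract lists "time to acute exacerbations, counts of acute exacerbations" among the Aim 2 primary outcomes. The body places exacerbations under Section 7.3.3.2 (Secondary Outcomes) and describes "The time to first exacerbation and population annualized counts of exacerbations". The two labels differ, but under either one exacerbations are an outcome of the matched oxygen comparison.

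Section 7.3 introduces Table 1 thus: "An overview of the analytic study variables and the study periods for which each analytic variable will be reported is provided in Table 1". The row "Acute exacerbations" is marked for claims, EHR and Aim 2 follow-up. The pre-index baseline is defined in the same section as "The 12-month period prior to the index date".

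The abstract's clinical covariates for Aim 2 are "underlying ILD type; respiratory diseases; other clinical characteristics; Quan-Charlson comorbidity score; AHRQ comorbid conditions; smoking; pulmonary rehabilitation", followed by utilization measures. Section 7.3.5.2 spells out the respiratory conditions: "pulmonary hypertension, acute respiratory failure, asthma, COPD, pneumonia, lung transplantation, upper respiratory tract infection, lower respiratory tract infection, lung cancer, and cystic fibrosis". Section 7.3.5.3 adds specialty visit days, medication classes, all-cause utilization and costs. None of these lists names a prior exacerbation.

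Section 7.2.3 refers to Section 7.6.2.2 for the matching, and Section 7.1 says that outcomes will be modelled with multivariable methods. Section 7.6.2 is not in the public text.

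**The concern.** Recent worsening is a plausible reason for starting oxygen and a plausible predictor of further exacerbations. Suppose initiators are matched to patients who look alike on the listed covariates but have had fewer exacerbations. The pre-existing difference would then carry into follow-up and could be read as harm from oxygen. Whether oxygen improves or worsens outcomes is the question that the plan sets itself in Section 5.

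A count from the same algorithm before index would also pick up a patient's habitual CT use and dyspnea coding. Both feed the outcome definition, and neither is a named covariate.

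**Working it through.** The plan gives no exacerbation rate, power or effect size, so there is no stated figure to reproduce. The check is first a reading of the text, then an illustration of scale.

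**Table 1, outcome rows**

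| Row | Pre-ILD baseline | Pre-index baseline | Aim 2 follow-up |
|---|---|---|---|
| Hypoxemia | X | X | X |
| Disease progression | – | – | X |
| Acute exacerbations | – | – | X |

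The table can show an outcome's baseline value, as it does for hypoxemia. A blank cell alone is not decisive: disease progression is blank at pre-index baseline, yet Section 7.3.3.1 captures FVC in that period. For exacerbations no such text exists. Section 7.3.3.2 defines only post-index measures, and Sections 7.3.5.1 to 7.3.5.3 and the abstract add none. The table, the outcome definition and the covariate lists therefore agree.

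**Proxies.** The listed variables nearest to exacerbation history are acute respiratory failure, pneumonia, lower respiratory tract infection, corticosteroid use, pulmonology visits, and all-cause ER and inpatient use, together with baseline hypoxemia from Table 1. The 7.3.3.2 rule is a CT scan with dyspnea in the preceding 30 days and no excluded cause. It requires no admission, and it rules out pulmonary infection, so the infection indicators mark events that the rule discards. The proxies overlap with exacerbation history but do not replace it.

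**Scale.** Let p1 and p0 be the proportions with a pre-index exacerbation in the oxygen and no-oxygen cohorts after matching, and r the ratio of later exacerbation rates with versus without such a history. With no true oxygen effect, the apparent rate ratio is

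[1 + p1(r − 1)] / [1 + p0(r − 1)].

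All inputs are assumptions; none comes from the documents. The main grid takes p1 of 0.20 to 0.40, p0 of 0.10 to 0.15 and r of 2 to 3.

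| Setting | p1 | p0 | r | Apparent rate ratio |
|---|---|---|---|---|
| Grid, lowest | 0.20 | 0.15 | 2 | 1.20/1.15 = 1.04 |
| Grid, intermediate | 0.30 | 0.10 | 3 | 1.60/1.20 = 1.33 |
| Grid, highest | 0.40 | 0.10 | 3 | 1.80/1.20 = 1.50 |
| Gap halved by proxies, lowest | 0.1875 | 0.1625 | 2 | 1.1875/1.1625 = 1.02 |
| Gap halved by proxies, highest | 0.325 | 0.175 | 3 | 1.65/1.35 = 1.22 |

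The halved rows shrink p1 − p0 by half around its midpoint. A second set of assumptions (10% vs 5%, 20% vs 10% or 30% vs 10%, with r from 1.5 to 3) gives 1.05/1.025 = 1.02 up to 1.33. The overall span is about 1.02 to 1.5.

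**The case against.** The strongest reply is that the decisive section is withheld. A reader might infer from the blank Table 1 cell that the variable will not exist at baseline, and hence that the oxygen comparison is not adjusted for it. The documents do not support either step. Section 7.6.2 would hold the matching and model covariates, and its absence from the public text is not an omission from the plan. Table 1 calls itself an overview and is visibly incomplete: besides the FVC example, the other clinical characteristics of Section 7.3.5.2 (reflux disease, heart failure, sleep apnea) have no row, although the abstract lists that group as Aim 2 covariates. This part of the reply stands in full.

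Three further points stand in part.

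- The proxies are more numerous than a quick reading suggests. They make the upper end of the range an extreme case but do not remove the gap.
- The algorithm cannot simply be carried back without thought. The Figure 2 notes allow the ILD diagnosis to fall within the pre-index baseline, so CT plus dyspnea in that window may be diagnostic work-up. This calls for a safeguard and is not a reason to leave history out.
- Section 7.8 already concedes residual confounding. The concession is general, while this particular confounder can be measured in data already held.

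**Conclusion.** The point holds in a limited form. The visible plan neither defines a pre-index exacerbation variable nor lists exacerbation history as a covariate, and whether the Aim 2 comparison adjusts for it cannot be confirmed from the public text. If it is left out, the likely direction of bias in the exacerbation outcomes is against oxygen, provided that initiators have had more prior exacerbations than their matches and that such a history raises the later rate. The size is unknown. The range of about 1.02 to 1.5 shows only what assumed inputs would produce, and its lower end is negligible. Some carry-over to mortality is conceivable, but the documents offer nothing from which to gauge it.

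The change is worth making because it is cheap. If 7.6.2 already includes exacerbation history, Table 1 and Section 7.3.5 still need to be brought into line with it.

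**What to change.** Confirm whether Section 7.6.2 already includes exacerbation history. If it does not:

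1. Apply the 7.3.3.2 algorithm to the 12-month pre-index baseline, ending the day before index, and mark that cell in Table 1.
2. Add to Section 7.3.5.2 the number of episodes (0, 1, 2 or more) and an indicator for any episode involving hospitalization.
3. Include both in the propensity score, and report their standardized differences after matching.
4. Adjust for the episode count in the time-to-first-exacerbation and count models.
5. Separate episodes around the ILD diagnosis date, or repeat the analysis without them, so that diagnostic work-up is not counted as exacerbation.

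The cost is a wording change and one more run of an algorithm that the study must program anyway, on claims and EHR data already required. No new data or patients are needed. The downside is one or two more covariates in the propensity model and possibly a few oxygen patients left unmatched.

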7.3.1 Aim 1 Outcomes

7.3.1.1 Primary Outcomes

- **Oxygen Therapy**—Evidence of oxygen use will be captured in the pre-ILD baseline and Aim 1 follow-up periods based on the presence of ≥ 1 diagnosis (ICD-10-CM), procedure (HCPCS, CPT), or revenue code for oxygen therapy. Among patients with oxygen therapy in follow-up, the following aspects of oxygen therapy will be described:
 - **Time to oxygen therapy initiation**—The time in days from the fibrosing ILD diagnosis date to oxygen therapy initiation, among patients without evidence of oxygen therapy in the pre-ILD baseline period.
 - **Sustained oxygen therapy use**—Using claims, sustained oxygen therapy use will be defined among patients with at least 12 months of follow-up after the index date (oxygen initiation date), as a binary variable for the presence of ≥ 11 claims for oxygen therapy in a 12-month period. The following aspects of sustained oxygen therapy will be described:
 - **Time to sustained oxygen therapy use**—The time in days between the index date and the earliest date that defined the sustained oxygen therapy use.
 - **Sustained oxygen therapy use within the first 12 months of follow-up**—The number of patients with the evidence of sustained oxygen therapy use during the first 12 months of follow-up.
 - **Note:** As a sensitivity analysis, sustained oxygen therapy use will also be defined as ≥ 6 claims for oxygen therapy in a 12-month period and, based on the distribution of the count of claims among the population, as the 75th percentile of claims in a 12-month period.

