5. RATIONALE AND BACKGROUND

Interstitial lung disease (ILD) is a broad term that describes more than 200 diverse lung disorders, including idiopathic pulmonary fibrosis (IPF), autoimmune ILD, hypersensitivity pneumonitis (HP), and sarcoidosis.¹ Typical symptoms of ILD include cough and dyspnea, as well as decreased lung capacity², which leads to exercise intolerance and hypoxemia.

The major goal of therapy in ILD patients is to slow disease progression as well as improve the associated dyspnea, exercise capacity, and health-related quality of life.³ Approved treatment options for fibrosing ILD comprise antifibrotic treatments including nintedanib and pirfenidone, which slow the rate of decline in forced vital capacity (FVC). Other commonly prescribed treatment options are corticosteroids, immunosuppressants, opioids, and lung transplantation.⁴ Despite advances in pharmacotherapy, many patients continue with disease progression. Oxygen therapy is commonly administered to reduce breathlessness and increase physical capacity by improving gas exchange.⁵

Supplemental oxygen (O₂) is commonly prescribed in clinical practice for patients with fibrotic ILD; however, robust evidence to support its long-term use is lacking. Recommendations for long-term oxygen therapy (LTOT) for resting hypoxemia in ILD are largely extrapolated from trials conducted in chronic obstructive pulmonary disease (COPD), where a survival benefit is well established.^{6,7} The American Association for Respiratory Care guideline recommends the use of oxygen therapy to maintain the oxygen saturation (SpO₂) range of 94–98% for most hospitalized patients.⁸ Despite its frequent use, there is a paucity of studies evaluating the incidence, prevalence, and impact of LTOT on outcomes such as disease progression or mortality in ILD. This study will help fill in the gaps in increasing the understanding of the use of oxygen therapy among fibrosing ILD patients and assess whether the use of oxygen leads to better or worse outcomes.

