7.2.3 Study population: Aim 2 [REDACTED]

The analysis for Aim 2 and Further Aim will include patients identified for Aim 1 in Section 7.2.2 who meet the following additional selection criteria. Final oxygen therapy cohorts will be determined during the propensity score matching (PSM) procedure outlined in Section 7.6.2.2.

- **Oxygen therapy cohort**

- ILD patients with ≥ 1 medical claim for oxygen therapy after fibrosing ILD diagnosis. The ***index date*** will be defined as the first date of a claim for oxygen therapy.

- **No oxygen therapy cohort**
 - Matched to a patient in the oxygen therapy cohort. The **index date** will be assigned as a date that is eligible to set an index date (i.e., similar to the matched oxygen therapy patient in time from the fibrosing ILD diagnosis date to the index date, and during the same continuous enrollment period as the fibrosing ILD diagnosis date).

NOTE: Following review of results from Aim 1, the study team will determine whether criteria for Aim 2 and Further Aim require revision.

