7.3.2 Aim 2 Exposures

The exposure of interest is oxygen therapy versus no oxygen therapy among patients with fibrosing ILD and is defined based on evidence of oxygen therapy following ILD diagnosis, as described in Section 7.2.3.

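### A single oxygen code from any care setting can set initiation and the Aim 2 index date, so follow-up may start on an acute event that matched controls do not share

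*Combined protocol and SAP*

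**What the plan says.** Three places define when oxygen starts, and they differ.

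- **Section 7.3.1.1 (Aim 1):** oxygen use, at baseline and in follow-up, needs only one diagnosis, "procedure (HCPCS, CPT), or revenue code for oxygen therapy". Time to initiation is then measured "among patients without evidence of oxygen therapy in the pre-ILD baseline period".
- **Section 7.2.3 (Aim 2 cohort):** at least one "medical claim for oxygen therapy after fibrosing ILD diagnosis", with the first such claim as the index date. Section 7.3.2 adds that exposure "is defined based on evidence of oxygen therapy following ILD diagnosis".
- **Section 7.3 (Aim 2 index date):** "the first date following the fibrosing ILD diagnosis date with a claim with diagnosis for oxygen therapy".

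None of the three mentions place of service, a second claim or a minimum duration. Section 7.4 says that the linked data include facility claims.

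Persistent use is handled separately. Sustained use is an Aim 1 outcome, defined "as a binary variable for the presence of ≥ 11 claims for oxygen therapy in a 12-month period" among patients with at least 12 months of follow-up after initiation. It has sensitivity definitions of at least 6 claims and of the 75th percentile of claims. It does not define the Aim 2 cohorts.

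**The concern.** Oxygen on a claim can mean the start of home oxygen or a short spell during an acute admission. The visible definitions treat the two alike. For Aim 1, initiation then mixes them, and one past hospital use at baseline removes a patient from the oxygen-naive group.

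The larger risk lies in Aim 2. If a hospital claim sets the index date, follow-up begins on the day the patient was ill enough to need oxygen. The matched control begins on a date chosen for its distance from ILD diagnosis, with no comparable event required. Death and acute exacerbation are both Aim 2 outcomes, and both are more likely just after an acute deterioration. An early excess in the oxygen cohort could therefore reflect the reason oxygen was given and not its effect.

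**Working it through.** **1. The plan's own count.** Section 7.5 and Table 3 give 34,299 adults with oxygen evidence. This is a database count, so only its consistency can be checked:

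- 214,725 / 1,179,017 = 18.2%
- 212,466 / 214,725 = 98.9%
- 80,151 / 212,466 = 37.7%
- 34,299 / 80,151 = 42.8%

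The counts fall at each step, and the text and table agree on 34,299. The oxygen criterion is again at least one piece of evidence, with no split by setting.

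**2. The definitions side by side.**

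| Place | Evidence that counts | Limit on setting |
|---|---|---|
| 7.3.1.1 | One diagnosis, procedure or revenue code | None visible |
| 7.2.3 | One medical claim | None visible |
| 7.3, index date | A claim with a diagnosis for oxygen | None visible |

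Read literally, a revenue code can set Aim 1 initiation but not the Aim 2 index date as Section 7.3 words it. Under Section 7.2.3 the same claim could set both.

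**3. Timing.** In Section 7.3 the pre-index baseline is the 12 months before the index date, and the index date is day 1 of follow-up. An event that starts on the index date is therefore outside the covariate window and inside the outcome window. Section 7.8 describes matched patients as alike on pre-ILD characteristics, and that window closes even earlier. Section 7.3.3.2 defines an exacerbation as a CT scan with dyspnea in the preceding 30 days and no listed alternative cause. A CT done during the admission that prompted the oxygen could meet this definition.

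**4. Illustration (all inputs assumed).** Let *s* be the share of the oxygen cohort whose only oxygen was acute. Let HR_o and HR_a be the hazard ratios against matched controls for ongoing and acute-only users. Early in follow-up, the cohort hazard ratio is approximately

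HR ≈ (1 − s) × HR_o + s × HR_a.

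For example, with s = 0.30: 0.70 × 0.80 + 0.30 × 1.5 = 0.56 + 0.45 = 1.01.

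| HR_o | HR_a | s = 10% | s = 30% | s = 50% |
|---|---|---|---|---|
| 0.80 | 1.0 | 0.82 | 0.86 | 0.90 |
| 0.80 | 1.5 | 0.87 | 1.01 | 1.15 |
| 1.00 | 1.0 | 1.00 | 1.00 | 1.00 |
| 1.00 | 1.5 | 1.05 | 1.15 | 1.25 |
| 1.00 | 2.0 | 1.10 | 1.30 | 1.50 |

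Applied to 34,299, these shares are about 3,430, 10,290 and 17,150 patients. That is an order of magnitude only, because the feasibility query used 6-month enrollment windows and not the study's own criteria. The formula ignores the earlier loss of acute-only patients through death, which would reduce their weight later in follow-up.

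**The case against.** Much of the opposing case has force.

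- **The question is initiation.** A reader might infer that one-code use is being passed off as long-term oxygen therapy, since Section 5 says "there is a paucity of studies evaluating the incidence, prevalence, and impact of LTOT on outcomes such as disease progression or mortality in ILD". The documents do not support that. The objectives in Section 6 concern oxygen therapy and its initiation, no variable is labelled long-term therapy, and sustained use is reported separately in Aim 1. For the same reason, initiation rates are not overstated merely because they include short use. This stands, but it does not touch the timing problem in Aim 2.
- **The relevant text is partly unseen.** The code lists in Annex 4 and the matching section (7.6.2.2, cited in Section 7.2.3) are not shown. A setting restriction, matching on hospital status or a sensitivity analysis could be there. The revenue-code wording belongs to the Aim 1 definition only. This stands and limits confidence.
- **Matching may absorb the difference.** Candidate covariates in Sections 7.3.5.2 and 7.3.5.3 include acute respiratory failure, pneumonia, heart failure, emergency visits and admissions. They help with illness that began before the index date, but not with illness that began on it.
- **The exacerbation rule excludes other causes.** Episodes with pulmonary infection, left heart failure or pulmonary embolism coded in the 30 days before the CT drop out. That removes some acute index events from this outcome, but mortality has no such filter.
- **The plan leaves room.** Section 7.2.3 allows the Aim 2 criteria to be revised after Aim 1, and Section 7.8 admits residual confounding. Neither mentions care setting or transient oxygen.

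**Conclusion.** The concern holds in a conditional form. On the visible text, one code or claim from any setting defines initiation and Aim 2 exposure. If hospital or emergency oxygen is captured, the index date can fall on an acute event that the baseline covariates do not cover and that controls need not share. Early deaths and exacerbations could then be attributed to oxygen.

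The size cannot be determined, because the documents give neither the share of hospital-based index claims nor the hazard of those patients. The table above shows only that moderate assumed values could move a protective estimate to or past the null. If acute-only users carry the same hazard ratio as ongoing users, there is no distortion. It would be wrong to infer that the Aim 2 result is certainly biased.

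The inconsistency between Sections 7.2.3, 7.3 and 7.3.1.1 depends on none of these assumptions and needs correcting in any case.

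**What to change.** 1. Reconcile Sections 7.2.3, 7.3 and 7.3.1.1 so that one stated set of code types defines both initiation and the Aim 2 index date. If the code lists or Section 7.6.2 already restrict the setting, say so in the definitions.
2. Report the share of index claims that arise in inpatient or emergency settings, before the Aim 2 outcomes are compared.
3. Keep the any-code definition as primary, which fits the initiation objective. Add a sensitivity analysis, for Aim 1 initiation and for the Aim 2 outcomes, in which only non-inpatient, non-emergency evidence sets initiation. In Aim 2, drop matched pairs whose index claim is inpatient or emergency instead of moving them to a later claim. Require controls to have no oxygen code from any setting up to their index date.

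The details in step 3 matter. Re-dating hospital starters to a later outpatient claim would require them to survive until that claim, which builds in immortal time. Without the rule for controls, patients treated with oxygen in hospital could enter the comparison group as untreated.

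The cost is a setting filter on claims already extracted, plus a smaller cohort and wider intervals in the sensitivity analysis. The primary analysis keeps its sample, apart from any change caused by settling on one set of code types.
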